12.1.9 Clinical Global Impression (CGI)

The CGI is a 3-item observer-rated scale that measures illness severity, global improvement or change and therapeutic response. A modified version of the CGI will be used in this trial to assess “illness” instead of “mental” illness. Investigators will complete the questionnaire at Visits 1 (Baseline), 2, 3, 4, 5, and results will be entered into the eCRFs by the site staff. A CGI can only be assessed during an on-site visit and not be assessed remotely.

12.2 Data Monitoring Committee (DMC)

An independent Data Monitoring Committee (DMC) will be established to monitor the safety of IMP throughout study BT – L-CsA – 201 – SCT. The DMC, represented by four members in total, three expert physicians in the field of BOS and one non-medical expert, will monitor safety by evaluating the safety analyses prepared by the independent DMC statistician during the course of the clinical trial. Details of the composition, meeting frequency and safety analyses will be included in the DMC’s Charter.

The DMC will evaluate treatment groups for possible trends in AEs, determine whether the basic clinical trial assumptions remain valid, evaluate whether the overall integrity, scientific merit and conduct of the clinical trial remain acceptable, and make recommendations to Sponsor.

Members of the DMC will be unblinded.

The DMC will perform a comparison between the rate of observed COVID-19 cases and rate of patients withdrawal among trial participants in both treatment arms.

DMC recommendations may include advice regarding continuation, modification, suspension or discontinuation of the trial based on safety (but not on efficacy) reasons. However, the final decision for trial continuation, modification, suspension or discontinuation rests solely with the Sponsor

13 VISIT SCHEDULE

All clinical trial visits, investigations and activities are listed in the Clinical Trial Schedule of Activities below. Further details on the methodology of these investigations and activities are described in detail in [Section 11](#) and [Section 12](#). The investigator will adhere to the visit and procedure schedule as closely as possible.

All patients assigned to a randomization number will be followed according to the protocol unless consent for follow-up is withdrawn. The Sponsor must be notified of all deviations from the protocol visit schedule or evaluations, and these visits/evaluations, if applicable, must be rescheduled or performed at the closest possible time to the original schedule.

Proper patient understanding and competency of the L-CsA **CCI** use will be ensured in an individual training by the responsible clinic personnel. The patient will be administering the drug independently under supervision to verify patient competency with the equipment and drug tolerability.

For emergency and other unscheduled visits to a medical facility other than the clinical trial site, medical records of the visit should be obtained by the Investigator.

If a patient prematurely discontinues clinical trial participation for any reason, e.g., the patient withdraws consent for further participation in the clinical trial, the evaluation listed under “End of Study Visit (EoS)” (Visit 6) should be completed prior to discontinuation whenever possible (the reason for premature withdrawal should always be documented).

Schedule of Activities

Clinical Trial Period	Screening	Treatment						Follow-Up
Visit Number	-	V 1	V 2	V 3	V 4	V 5 / EOT	Remote Visits	V 6 / EoS
Week & Window	W -4 to W 0	W 0 Day 1	W 2 ± 3 Days	W 4 ± 3 Days	W 8 ± 7 Days	W 12 ± 7 Days	V3, V4 and V6 can be performed remotely	W 14 ± 3 Days
Informed Consent ¹	X							
Demographics/Medical History	X	-						
Inclusion/Exclusion criteria	X							
Serum/Urine Pregnancy Test	X	X	X	X	X	X		X
Physical Examination ²	X	X	X	X	X	X		X
Vital signs ³	X	X	X	X	X	X		X
Clinical Laboratory Tests ⁴	X	X	X	X	X	X		X
PK Blood Sampling ⁵		X	X	X	X	X		
Spirometry ⁷	X	X ⁶	X ⁶	X ⁶	X ⁶	X ⁶		
Randomization		X						
SF-36		X	X	X	X	X	X ⁸	
CGI Questionnaire		X	X	X	X	X		
Investigator's Tolerability Assessment				X		X		
Local IMP Tolerability		X	X	X	X	X		
IMP Administration				Twice daily administration			X	
Concomitant Medication	X	X	X	X	X	X	X	X
Adverse Events	Permanent assessment throughout the complete clinical trial period							
Drug Accountability/IMP availability check			X	X	X	X	X	

¹ Conduct prior to any screening activities.

² Including body weight and height (at Screening visit only), cardiovascular, respiratory, nervous, gastrointestinal, hepatic, renal, dermatological, musculoskeletal, extremities, eyes, ears, nose, throat, and lymphatic.

³ Including systolic and diastolic blood pressure (sitting, after minimum 5 minutes of rest), pulse rate (sitting, after min. 5 minutes of rest), body temperature (the same method should be used for each patient and throughout the clinical trial), and respiratory rate.

⁴ According to [Section 12.1.6](#).

[figure not shown]
⁵ Day 1 blood samples at pre-dose, directly after end of inhalation, 15, 30, 45 min (+/- 5 minutes), and 1, 1.5, 2, 4 h (+/- 15 minutes), after end of inhalation. Other visits are a trough (pre-dose – 15 min before inhalation) sample only.

⁶ According to [Section 11.1.1](#).

⁷ Spirometry results at screening visit are required to confirm BOS diagnosis. The assessment is allowed to be performed +/- 2 days from screening visit date (but has to be performed after informed consent was given by the patient).

⁸ applicable for remote Visits 3 and 4 only

13.1 Clinical Trial Flow Chart

13.2 Visits

13.2.1 Screening

Eligible patients who express interest in participating in the trial must sign an EC approved informed consent form (ICF) prior to initiation of any clinical trial activities. Patients who fulfill all of the inclusion criteria and none of the exclusion criteria may be enrolled into the clinical trial.

Documentation of the patient's consent and eligibility must be completed by the Investigator or his/her designee. All patients who fail the screening activities will be documented in the screening failure log. Re-screening of patients can be considered.

The following screening activities will be performed during the screening visit (up to 4 weeks prior to Visit 1):

- **Informed Consent:** Obtain informed consent prior to performing any clinical trial activities.
- **Demographics:** Year of birth, gender, ethnic group.
- **Medical History:** Details related to each patient's allo-HSCT will be recorded and will include: underlying condition (reason for HSCT), date, type of transplantation, donor demographics, donor/recipient human leukocyte antigen status, donor/recipient cytomegalovirus status, donor/recipient Epstein Barr virus status. All other significant medical conditions and procedures (including past surgeries, documentation of cGvHD in another organ) occurring before the ICF is signed will be recorded as medical history
- **Diagnosis of BOS:** Historical spirometry values documented in the patient file will be used for the calculation of decline $\geq 10\%$ predicted in FEV₁ over 24 months as requested in the Inclusion criteria. Date of first diagnosis of BOS will be documented.
- **Inclusion/Exclusion Criteria:** Evaluate eligibility for the clinical trial per the inclusion/exclusion criteria.
- **Serum/Urine Pregnancy Test:** Will be obtained in women of childbearing potential unless there is documented infertility.
- **Physical Examination:** Body weight and height (at Screening only), cardiovascular, respiratory, nervous, gastrointestinal, hepatic, renal, dermatological, musculoskeletal, extremities, eyes, ears, nose, and throat, and lymphatic.
- **Vital Signs:** Blood pressure, pulse rate, body temperature, respiratory rate.
- **Clinical Laboratory Tests:** All parameters listed in [Section 12.1.6](#) of the protocol, to be performed in the local laboratory at the site.
- **Spirometry:** FEV₁, FVC, FEV₁/FVC according to ATS/ERS standards.
- **Concomitant Medications/Therapies:** Name of drug, dosage, start date, stop date, indication
- **AEs**

13.2.2 Visit 1 / Baseline Visit / Randomization

Baseline Prior to Start of Treatment

- Verify Informed Consent was obtained
- Verify Demographics/Medical History
- Repeat Urine/Serum Pregnancy Test (Urine samples can be collected at the Randomization Visit in order to obtain results quickly while the patient is in the clinic and not delay randomization)
- Physical examination
- Vital signs
- Clinical laboratory tests
- PK blood sample pre-dose
- Spirometry
- Randomization
- Concomitant medications/therapies
- AEs
- CGI (Item 1 only)
- SF-36 questionnaire

Start of Treatment

Following activities will be performed:

- Train patient on L-CsA **CCI** use, drug storage, and inhalation technique
- IMP Administration. Supervise first inhalation for proper use of the nebulizer and for tolerability issues.
- Verify patient is familiar with drug administration and use of nebulizer device
- Emphasize importance of adherence to IMP
- Emphasize importance of adherence to usual medications as taken prior to participating in the trial
- Spirometry: (1 hour \pm 20 minutes after completion of dosing with IMP)
- PK blood samples directly after end of inhalation, 15, 30, and 45 minutes (+/- 5 min), and 1, 1.5, 2, and 4 hours (+/- 15 min.) after end of inhalation
- Local IMP tolerability

Prior to release from clinic, study drug and the nebulizer system for home use will be dispensed to each patient. Patient will receive full IMP supply for the 12 weeks treatment period.

13.2.3 Visit 2 through Visit 5 / EoT

- Physical examination
- Vital signs
- Clinical laboratory tests
- Cyclosporine A whole blood trough levels (blood sample pre-dose)
- Urine/Serum pregnancy test
- Spirometry
- IMP Administration
- Concomitant medications/therapies
- AEs
- CGI (Items 1-3)
- SF-36 questionnaire
- Local IMP tolerability
- Drug Accountability by vial count (Visit 5 only)
- Check IMP supplies of patient

13.2.4 Visit 3 and Visit 5

- In addition to the assessments described in section 13.2.3, the clinical investigator will perform an Investigator's Tolerability Assessment assessed by means of a five-point verbal rating scale with the response options 'very good', 'good', 'satisfactory', 'moderate', and 'poor'.

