8.3.2.3 Administration of IMP

In clinical trials 12011.201 and clinical trial AI 001 totaling > 1100 patient months of exposure, L-CsA was well tolerated. Patients will be educated regarding use of the L-CsA **CCI** and administration of the first dose will be observed. At subsequent study visits, it will be requested that the patient self-administer a dose of IMP while observed by study personnel.

Each patient will receive two IMP administrations per day, one in the morning and one in the evening. The inhalations are scheduled to be taken approximately 12 hours (but not less than 6 hours) apart, e.g., at 8:00 a.m. and 8:00 p.m. each day. Instructions for administration should be followed as described in the Instructions For Use.

Handling of IMP Inhalation:

Each patient will open a glass vial by lifting up the plastic disk/cap, lifting up the metal flap to remove the metal ring, metal cap, and the rubber stopper. The plastic ampoule containing 1.2 ml or 2.4 mL of the 0.25% NaCl as solvent will be opened by twisting the head part several times in one direction. The NaCl solution will be squeezed into the glass vial containing the whitish lyophilisate cake. The glass vial will be re-closed with the rubber stopper and swirled gently without spilling any liquid for a minimum of 1 minute and up to 5 minutes, until the visible particles are completely dissolved. Shaking of the vial must be avoided to prevent foaming of the reconstituted solution.

Next, the reconstituted IMP should be poured into the L-CsA **CCI** chamber. The nebulizer should be kept horizontal during operation. During inhalation, the patient should sit in an upright position and inhale and exhale deeply through the mouthpiece of the nebulizer without interruption until nebulization shuts off automatically. The solution is for single use only, and no remaining solution should be left in the glass vial. All other clinical trial materials, including unused IMP, must be brought back to the clinical trial center at each scheduled visit for drug and device accountability. After completion of the inhalation, the patient should remove all excess IMP in the mouth and pharynx by rinsing and gargling with water and subsequently discharging the solution.

Interruption of IMP Inhalation:

If a patient needs to temporarily interrupt IMP inhalation (e.g., due to coughing), the patient should turn off the device and turn it back on when ready to resume inhalation.

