8.6 Investigational Medicinal Product: Supply and Accountability

Each Investigator is responsible for ensuring that deliveries of IMP vials and boxes, L-CsA CCI and other clinical trial materials are correctly received and recorded, that these are handled and stored safely in a locked and temperature controlled storage place with access for authorised study staff only and that they are used in accordance with this protocol. In addition, the Investigator will monitor each patient's treatment compliance by counting the used/unused drug vials at each visit.

For the purpose of this trial patients will be regarded as compliant if no more than 45 vials of IMP over the entire treatment period of 12 weeks are returned as unused – this corresponds to approximately 75% treatment compliance. The reason for non-compliance shall be documented according on the respective eCRF.

Unused IMP vials, ampoules, boxes, and L-CsA CCI must be returned or destroyed on-site after accountability has been completed and destruction is approved by Zambon SpA. A list of IMP, L-CsA CCI, and other materials received, used, returned, or destroyed must be prepared, completed and signed by the Investigator; any discrepancies must be accounted for.

COVID-19 specific consideration: the patients will be supplied during V1 with the full amount of study medication needed, to cover the total treatment period of 12 weeks. Patient has to bring all study medication back to the site at EoT Visit V5 for Drug Accountability.

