9.3.1 Procedures of Patient Withdrawal and IMP discontinuation

Withdrawal:

The patient is free to withdraw from the clinical trial for any reason and at any time without giving a reason for doing so and without penalty or prejudice. The Investigator is also free to terminate a patient's involvement in the clinical trial at any time if the patient's clinical condition warrants it. In case of early withdrawal, the patient will be encouraged to perform a final visit. The final visit will encompass the assessments listed under EoS Visit ([Section 13.2.5](#)).

Additionally, used and unused IMP and inhalation device will be retrieved, if applicable. Zambon SpA will be notified by the Investigator via entry in and notification by the eCRF that the patient has terminated clinical trial participation.

IMP discontinuation

The Investigator or patient is free to discontinue regular intake of IMP, if the clinical condition of the patient or other serious reasons warrant it. Reasons for discontinuation of IMP may include (but are not limited to) the following:

- Significant respiratory infection requiring therapy
- Respiratory failure from any cause
- Mechanical ventilation

If 10 or more consecutive doses of IMP are missed, regardless of reason, then IMP will be considered as discontinued and should not be resumed. If IMP inhalation is discontinued, the patient will be asked to return for clinical trial visits according to the visit schedule defined in the protocol but shall not receive IMP.

Stopping criteria are outlined in detail in [Section 8.5.1](#).

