12.1.4.3 Investigational Medicinal Product (IMP) Overdosing

An overdose is a deliberate or inadvertent administration of a treatment at a dose higher than specified in the protocol. For the purposes of this clinical trial, any dose of aerosolized IMP administered to a patient that exceeds the dose foreseen in the protocol by more than 50% over 4 weeks should be reported as an overdose. Any occurrence of overdose are to be reported through the SAE procedures described above.

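### Protocol sections conflict on when study-drug vials are counted, and the single whole-period compliance ratio in SAP 16.2 can hide an excess in the first 4 weeks

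*Protocol*

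**What the plan says.** **When vials are counted or returned**

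- Protocol 13.2.3 (Visits 2 to 5): "Drug Accountability by vial count (Visit 5 only", and separately "Check IMP supplies of patient", with no number to be recorded.
- Protocol 8.6, main text: the investigator monitors compliance by "counting the used/unused drug vials at each visit".
- Protocol 8.6, COVID-19 paragraph: "Patient has to bring all study medication back to the site at EoT Visit V5 for Drug Accountability".
- Protocol 8.3.2.3: trial materials, "including unused IMP, must be brought back to the clinical trial center at each scheduled visit for drug and device accountability".
- Synopsis: vials come to Visit 2 and to on-site Visits 3 and 4, but for an availability check.
- Schedule of Activities: accountability and availability check share one row, marked at Visits 2 to 5 and at remote visits.

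**Supply.** Protocol 13.2.2: "Patient will receive full IMP supply for the 12 weeks treatment period". Section 8.4.3, partly redacted, still describes a monthly supply at each later clinic visit.

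**Rules that depend on dosing over time.** Under 12.1.4.3, dosing that "exceeds the dose foreseen in the protocol by more than 50% over 4 weeks should be reported as an overdose" goes through the SAE procedures. Section 9.3.1 begins its discontinuation rule with "If 10 or more consecutive doses of IMP are missed". Neither section names a data source or a time at which the rule is checked.

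**Analysis.** SAP 16.2 confirms exposure from vials dispensed minus unused vials returned, and from dosing in the eCRF. Vials not returned count as used. Compliance is one ratio from baseline to EoT, in the bands <50%, 50-79%, 80-120% and >120%.

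**The concern.** The protocol gives sites incompatible instructions. A site can follow the visit checklist in 13.2.3, make no count before Visit 5, and believe that it complies. Patients hold the whole supply at home from Visit 1, so no re-dispensing step forces an earlier reckoning.

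The overdose rule works over 4 weeks, and the primary assessment covers the first 4 weeks. A single total at week 12 answers neither on its own time scale. SAP 13.1 and 13.3.1 do give incidence densities by visit interval, but their denominators are days, not doses taken. With 8 patients planned per arm, one misdosed patient is 1/8 = 12.5% of an arm. If that patient's early exposure is not visible, events are read against the assigned strength, which weakens the 5 mg versus 10 mg tolerability comparison.

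**Working it through.** **Inputs.** Two inhalations a day (8.3.2.3) for 12 weeks. Compliance limit of 45 unused vials, stated as about 75% (8.6). Overdose threshold of more than 50% over 4 weeks (12.1.4.3). Ten consecutive missed doses (9.3.1). Boxes of 60 vials (8.4.1). Visits at weeks 0, 2, 4, 8 and 12, with windows of 3 days at Visit 3 and 7 days at Visit 5. The number of vials dispensed is not stated; I assume a range from 168 (exact need) to 180 (three boxes).

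**The plan's own figure.** Scheduled doses = 12 × 7 × 2 = 168. Compliance at the limit = 1 − 45/168 = 73.2%, or 1 − 45/180 = 75.0%. Both agree with the stated figure of about 75%.

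**Overdose threshold.** 4 × 7 × 2 = 56 doses; 1.5 × 56 = 84; the first reportable number is 85; 85/56 = 152%.

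**What the single SAP ratio shows** (doses used / 168):

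| Pattern | Weeks 1-4 | Weeks 5-12 | Total | Ratio |
|---|---|---|---|---|
| Excess, then two a day until 168 vials run out | 85 (152% of 56) | 83 (74% of 112) | 168 | 100% |
| Excess, then two a day until 180 vials run out | 85 (152% of 56) | 95 (85% of 112) | 180 | 107% |
| One run of 10 missed doses, then resumed | – | – | 158 | 94% |

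All three fall in the 80-120% band. The first two need no deliberate under-use. At two a day after week 4, supply ends at day 28 + 83/2 = 69.5 or 28 + 95/2 = 75.5.

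**Timing.** If Visit 5 is the only count, a week 1-4 excess first shows in a count at about day 84 (77 to 91). A count at a Visit 3 on day 28 would show it 56 days sooner (49 to 63).

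**Limit of a Visit 3 count.** If Visit 3 falls on day 31, a patient who took 85 in 28 days and then two a day has used 85 + 6 = 91 against 62 scheduled, or 147%. The count must be read against actual days and prompts a check; it does not decide the rule.

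**What a supply check could show at week 4.** Vials left: 168 − 85 = 83, or 180 − 85 = 95. Weeks 5 to 12 need 112. The shortfall is 29 or 17 vials.

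**Missed-dose rule.** Ten doses are 10/2 = 5 days, while visits are 14, 14, 28 and 28 days apart. A count gives a total, not a sequence, so no vial count at these visits can show a consecutive run.

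**The case against.** A reader might infer that the overdose and missed-dose rules cannot be triggered in time. The documents do not support that. It takes one side of a contradiction as the whole protocol: 8.6 does require a count at each visit, and 8.3.2.3 does require unused product back. Vials are brought to on-site Visits 2 to 4 and supplies are checked, and at week 4 the patient above would be visibly 17 to 29 vials short. Protocol 14.2.3.1 also uses dosing recorded in the eCRF. SAP 16.2 lists administration dates and times and counts exposure days, which presupposes dated records. Neither rule makes a vial count its trigger.

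The stakes can also be called small. Protocol 6.1.5 reports no overdose-related event in earlier trials, local tolerability events are actively solicited (12.1.5), and the analysis is descriptive.

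Most of this stands: detection is possible. But a supply check with no recorded number does not secure it, and remote checks are made only as far as possible (13.2.7). The schedule lists no dosing diary, and no section says how or when home doses reach the eCRF. Central CsA levels are not available for immediate safety assessment (12.1). Good AE collection does not show what dose was taken. The masking in SAP 16.2 would also remain even if every site counted at every visit.

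**Conclusion.** The point holds as an internal contradiction plus a reporting gap. Sections 13.2.3 and 8.6 (main text) cannot both be followed, and a site that follows 13.2.3 leaves detection of a 4-week excess to unquantified supply checks and eCRF dosing entries whose capture is undescribed. Separately, the single ratio in SAP 16.2 shows an excess of 152% in weeks 1 to 4 as 100% to 107% overall, and nothing reports exposure in the primary window.

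The masking result assumes 168 to 180 vials dispensed. The documents give no overdose frequency, so the chance of such a case is unknown. This is a cheap improvement, not a threat to the trial's conclusions.

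Two further inferences should not be drawn. Moving the count would not make the 10-missed-doses rule workable, because that rule needs dated records. Nor does it matter that the >120% band could not be filled from the count: that depends on the assumed 180 vials, and an empty table category does no harm.

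**What to change.** 1. Reconcile 8.3.2.3, 8.4.3, 8.6 (both paragraphs), 13.2.3 and the Schedule of Activities, and split the combined schedule row into accountability and availability check.
2. Count the vials that patients already bring to on-site Visits 2, 3 and 4, and enter the number in the eCRF. At remote visits, record the patient's own count and flag it as such.
3. State which record and which time points are used to apply 12.1.4.3, reading each count against the actual days in the interval.
4. State that 9.3.1 is applied from dated dosing or interruption records in the eCRF, and describe how home doses are captured there.
5. In SAP 16.2, tabulate exposure and compliance by visit interval, at least Visit 1 to Visit 3 and Visit 3 to Visit 5, beside the whole-period ratio.

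The overdose and missed-dose rules are left unchanged.

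Cost: protocol wording, one eCRF field per visit, a few minutes of site time and one table, with no extra visit or supply. Patient-reported counts at remote visits will be less exact. Item 4 may cost more if home doses are not yet recorded with dates.
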